## 3.3 METHODOLOGY AND CONVENTIONS

Safety and efficacy data will be summarized and presented by treatment group (SGX942 and placebo) in summary tables. Continuous variables will be presented by descriptive statistics including n, mean, standard deviation, median, minimum, and maximum. Categorical variables will be tabulated by frequency count and percentage.

Unless otherwise stated, all statistical tests will be two-sided hypothesis tests performed at the 5% level of significance for main effects, and all confidence intervals will be two-sided 95% confidence intervals. All analyses will be performed using SAS® Version 9.3 or higher.

# 3.4 ADDITIONAL DATA HANDLING RULES AND PRESENTATION SPECIFICATIONS

The following general guidelines will apply to all statistical analyses and data presentations:

• Baseline is defined as the last available value obtained prior to the first dose of study drug, radiation and chemotherapy but within 96 hours of the initial drug treatment unless otherwise specified in this SAP.

Systeme Internationale (SI) units will be used for laboratory value presentations.

Age is calculated as of date that the informed consent form was signed.

- age = the integer part of ((date of informed consent – birth date+1)/365.25)

Body weight, height and temperatures will be converted using the following formula:

- kg = 1b/2.2
- -cm = 2.54 x in
- $^{\circ}C = (5/9) \times (^{\circ}F 32)$

All percentages will be rounded to one decimal place and lined up by the decimal place. The percentage will be suppressed when the count is zero.

Any p-values will be rounded to three decimal places and will be presented as '<0.001' if they are less than 0.001 after rounding.

For continuous variables that are recorded as "<X" or ">X", the value of "X" will be used in the calculation of summary statistics. The original values will be used for the listings.

Decimal places will be presented as follows:

- n: integer
- minimum and maximum: same precision as in the database
- mean and median: one more decimal place than minimum and maximum
- standard deviation: two more decimal places than minimum and maximum

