Randomization		X																
History of Pain and Opioid Use		X	2X	2X	2X	2X	2X	2X	2X	2X	2X	X	X	X	X		X	X
Assessment of Infections		X	2X	2X	2X	2X	2X	2X	2X	2X	2X	X	X	X	X			
Radiation ⁶			5X	5X	5X	5X	5X	5X	5X									
Cisplatin ⁶			X			X			X									
Administer Drug			2X	2X	2X	2X	2X	2X	2X	2X	2X							
WHO OM ⁷		X	2X	2X	2X	2X	2X	2X	2X	2X	2X	X	X	X	X			
PEG Tube Use		X	2X	2X	2X	2X	2X	2X	2X	2X	2X	X	X	X	X			
VS ⁸	X	X	2X	2X	2X	2X	2X	2X	2X	2X	2X	X	X	X	X			
Physical Exam	X	X									X^{13}				X			
Safety Labs ⁹	X	X^{12}			X			X			X ¹³		X		X			
AEs		X	2X	2X	2X	2X	2X	2X	2X	2X	2X	X	X	X	X			
Tumor Scan ¹⁰	X ¹¹																X	X
Serum Pregnancy	X	X ¹²	_		_		_					_			X			
HPV Status	X^{11}																	
Quality of Life		X				X					X^{13}							

¹Post-RT = time from the last radiation therapy treatment

Confidential Original: 11 January 2017

Amendment 1: 29 November 2017 Amendment 2: 22 January 2018 Amendment 3: 17 September 2019 ¹⁰ Scan = obtain initial staging CT/PET/MRI scans (screening scan must be within 6 weeks prior to Baseline)

² Baseline information needs to be obtained prior to (0 to 96 hours before) the first dose of study drug

 $^{^{3}}$ w = weeks

⁴Only to be done if WHO score is ≥2 at Week 4 Post-RT visit

⁵ m = months; patient contact (clinic visit, telephone, or email) required monthly through the 12-month clinic visit

⁶ Timing of radiation and chemotherapy at discretion of primary care physicians ⁷ WHO OM = oral mucositis grading with WHO Oral Mucositis Grading system

⁸ Vital signs to include temperature, weight, pulse, respirations, and seated blood pressure; Height will be obtained at Baseline only

⁹ Safety labs = hematology and clinical chemistry panels

¹¹ Need to confirm that the initial diagnostic scans were CT, PET, or MRI and the tumor was tested for HPV status

¹² Repeat test required if Baseline sample >7 days from Screening

¹³ To be done only on the second visit in week 2 post-RT

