6.2.5 Laboratory Assessments

6.2.5.1. **Serum Pregnancy Test**

Blood samples will be obtained at the Screening, Baseline (if Baseline >7 days from Screening), and 6 weeks post-RT visits for a serum pregnancy test (human chorionic gonadotropin [HCG]) for all women who are of childbearing potential.

6.2.5.2. **Hematology Tests**

The hematology panel will be performed at the Central Laboratory on samples collected at Screening, Baseline (if Screening tests were obtained >7 days from Baseline), Week 3, Week 6, and at the 2-week post-RT, the 4-week post-RT visit and the 6-week post-RT visits. The panel will consist of the following tests:

- Red blood cell count (RBC)
- Hematocrit
- Hemoglobin
- RBC indices
- Platelet count
- White blood cell count (WBC)
- WBC differential count

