6.3. Visit Schedule

6.3.1 Screening

The Screening visit must be done within 4 weeks prior to the Baseline visit. Prior to starting the study medication, the results of all tests must be reviewed to assure that the patient meets all entry criteria. Procedures to be done at this visit are:

- Obtain Informed Consent Form (ICF) signature
- Assure that the initial tumor imaging is compatible with RECIST Criteria (CT, MRI, or PET scans)
- Assure that the tumor was evaluated for HPV status
- Assessment of entry criteria
- Complete Medical History
- Complete Physical Examination
- Vital Signs
- Serum HCG pregnancy test (women only)
- Hematology Panel
- Clinical Chemistry Panel

6.3.2 **Baseline Day**

Baseline assessment will be completed prior to radiation, chemotherapy, and study drug administration but within 96 hours of the initial study drug treatment. Patient will be seen on the first day of study drug treatment. The entry criteria will be reviewed and an interim medical history taken to assure that the patient meets all entry criteria. If the patient still qualifies, they will undergo the following procedures:

Confidential

- Interim Medical History
- Randomization
- Vital signs
- Adverse events (begin collecting after randomization)
- Physical Exam
- Hematology Panel (if more than 7 days from Screening sample)

- Clinical Chemistry Panel (if more than 7 days from Screening sample)
- Clinical evaluation of mucositis (WHO Score)
- Quality of Life assessment
- Serum Pregnancy (if more than 7 days from Screening sample)
- History of pain and opioid medication use
- Assessment of Infections

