**Table 1: Schedule of Events by Week** 

Study week	Screen	Base 	1w 	2w	3w	4w	5w	6w	7 w	8w	9w	10w	11w	12w	13w	15- 55 w	19w	59w
Post-RT 										1w	2w	3w	4w	5w 	6w	2m-11 m 	12w	12m
Medical History	X	X	2X	2X	2X	2X	2X	2X	2X	2X	2X	X	X	X	X	X	X	X
Informed Consent	X																	
Randomization		X																
History of Pain and Opioid Use		X	2X	2X	2X	2X	2X	2X	2X	2X	2X	X	X	X	X		X	X
Assessment of Infections		X	2X	2X	2X	2X	2X	2X	2X	2X	2X	X	X	X	X			
Radiation 			5X	5X	5X	5X	5X	5X	5X									
Cisplatin 			X			X			X									
Administer Drug			2X	2X	2X	2X	2X	2X	2X	2X	2X							
WHO OM 		X	2X	2X	2X	2X	2X	2X	2X	2X	2X	X	X	X	X			
PEG Tube Use		X	2X	2X	2X	2X	2X	2X	2X	2X	2X	X	X	X	X			
VS 	X	X	2X	2X	2X	2X	2X	2X	2X	2X	2X	X	X	X	X			
Physical Exam	X	X									X 				X			
Safety Labs 	X	X 			X			X			X 		X		X			
AEs		X	2X	2X	2X	2X	2X	2X	2X	2X	2X	X	X	X	X			
Tumor Scan 	X 																X	X
Serum Pregnancy	X	X 													X			
HPV Status	X 																	
Quality of Life		X				X					X 							

<sup>1 Post-RT = time from the last radiation therapy treatment

<sup>2 Baseline information needs to be obtained prior to (0 to 96 hours before) the first dose of study drug

 $^{3}$  w = weeks

<sup>4Only to be done if WHO score is ≥2 at Week 4 Post-RT visit

<sup>5 m = months; patient contact (clinic visit, telephone, or email) required monthly through the 12-month clinic visit

<sup>6 Timing of radiation and chemotherapy at discretion of primary care physicians

<sup>7 WHO OM = oral mucositis grading with WHO Oral Mucositis Grading system

<sup>8 Vital signs to include temperature, weight, pulse, respirations, and seated blood pressure; Height will be obtained at Baseline only

<sup>9 Safety labs = hematology and clinical chemistry panels

Scan = obtain initial staging CT/PET/MRI scans (screening scan must be within 6 weeks prior to Baseline)
 Need to confirm that the initial diagnostic scans were CT, PET, or MRI and the tumor was tested for HPV status

 Repeat test required if Baseline sample >7 days from Screening 13 To be done only on the second visit in week 2 post-RT

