#### 10.2 CLINICAL LABORATORY PARAMETERS

Descriptive statistics for laboratory values (in SI units) and changes from baseline at each assessment time point will be presented by treatment group for the following laboratory parameters:

- Serum pregnancy test: human chorionic gonadotropin (HCG)
- Hematology: red blood cell count (RBC), hematocrit, hemoglobin, RBC indices, platelet count, white blood cell count (WBC), and WBC differential count
- Chemistry: serum sodium, serum potassium, serum chloride, serum bicarbonate (CO2), alanine aminotransferase (ALT), aspartate aminotransferase (AST), total bilirubin, alkaline phosphatase, total protein, serum creatinine, and blood urea nitrogen (BUN)

Laboratory values will be classified as "normal", "low", or "high" based on the central laboratory's normal ranges. Shift tables for each parameter will be tabulated by treatment group.

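### The SAP's 96-hour baseline window conflicts with the 7-day rule for repeating baseline labs, so some protocol-compliant patients have no laboratory baseline on a literal reading

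*SAP*

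**What the plan says.** SAP 3.4 gives one general definition of baseline: the last available value "prior to the first dose of study drug, radiation and chemotherapy but within 96 hours of the initial drug treatment". It leaves room for exceptions with the words "unless otherwise specified in this SAP".

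The rules for drawing laboratory samples use a different window:

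- Protocol 6.2.5.2 (hematology) schedules a sample at "Baseline (if Screening tests were obtained >7 days from Baseline", and 6.2.5.3 puts the same condition on chemistry.
- The Baseline Day list in Protocol 6.3.2 makes both panels conditional in the same way, for example "Hematology Panel (if more than 7 days from Screening sample".
- SAP Table 1, footnote 12, carries the rule into the SAP: "Repeat test required if Baseline sample >7 days from Screening".

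Two further windows matter. Protocol 6.3.1 states: "The Screening visit must be done within 4 weeks prior to the Baseline visit". Footnote 2 to the schedule of events (Protocol Table 7) states: "Baseline information needs to be obtained prior to (0 to 96 hours before) the first dose of study drug". SAP Table 1 repeats that footnote.

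For the analysis, SAP 10.2 requires that laboratory "changes from baseline at each assessment time point will be presented by treatment group", together with shift tables. It gives no separate definition of a laboratory baseline. Protocol 11.1.3 asks for the same summaries.

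**The concern.** The 7-day rule runs back from the Baseline visit, and the 96-hour rule runs back from first study drug. A Screening sample can be recent enough to need no repeat and yet too old to count as baseline. For such a patient the protocol collects no other pre-treatment sample, so the SAP definition returns nothing.

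Change from Baseline in hematology and chemistry is a listed safety endpoint, in patients receiving cisplatin at 80-100 mg/m². Applied as written, SAP 3.4 would discard pre-treatment values that the protocol accepts. The change and shift tables would then contain only patients screened very close to dosing or more than a week before Baseline. If the wording is instead left to interpretation, the choice of baseline falls to whoever programs the tables.

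**Working it through.** No sample size, power or alpha figure bears on this point, so there is no stated figure to reproduce. The check is arithmetic on the windows.

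**Definitions**

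- s = days from the Screening lab to the Baseline visit. The permitted range is 0 to 28 (Protocol 6.3.1).
- b = days from the Baseline visit to first study drug. The permitted range is 0 to 4 (96 hours; schedule footnote 2, Protocol 6.3.2).
- No repeat lab is drawn if s ≤ 7.
- The Screening lab meets SAP 3.4 only if s + b ≤ 4.

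**Who is affected.** A patient has no literal laboratory baseline when s ≤ 7 and s + b > 4.

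- With b = 0, this covers s above 4 and up to 7 days. Example: Screening labs 5 days before a same-day Baseline and first dose.
- With b = 4, it covers s above 0 and up to 7 days.
- The oldest unrepeated sample is 7 + 4 = 11 days before first drug.

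Same-day Baseline and first dose cannot be assumed for everyone. Baseline must precede radiation and chemotherapy, study drug may start up to 3 days after radiation begins, and it is not given on a chemotherapy day (Protocol 6.1, 6.3.2). Where cisplatin comes before the first study drug dose, b is at least about 1.

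**How many.** The documents do not give the distribution of s. As an assumption, let s be uniform on 0 to S days. For a fixed b,

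share = [min(7, S) − (4 − b)] / S, not less than 0.

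Counts are scaled to the planned 260 patients for illustration.

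| S (days) | b = 0 | b = 2 | b = 4 |
|---|---|---|---|
| 28 | 3/28 = 10.7% (28) | 5/28 = 17.9% (46) | 7/28 = 25.0% (65) |
| 14 | 3/14 = 21.4% (56) | 5/14 = 35.7% (93) | 7/14 = 50.0% (130) |
| 7 | 3/7 = 42.9% (111) | 5/7 = 71.4% (186) | 7/7 = 100% (260) |
| 4 | 0/4 = 0% (0) | 2/4 = 50.0% (130) | 4/4 = 100% (260) |

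The share is 0% under any distribution in which every Screening lab is either more than 7 days before Baseline (so repeated) or within 96 hours of first drug (so accepted).

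**What is not affected.** Protocol 6.3.2 collects the WHO score, quality of life, pain and opioid history and vital signs at Baseline with no 7-day condition. Their baselines fall inside the 96-hour window.

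**The case against.** The strongest reply is that the SAP does specify otherwise. SAP 3.4 calls its rules general guidelines and allows exceptions. SAP Table 1 places safety labs in the Baseline column and requires a repeat only beyond 7 days, so the natural reading is that a Screening sample up to 7 days old serves as the Baseline sample. On that view the 96 hours only restates the Baseline visit window and was never meant to remove labs that the schedule accepts.

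This may well be what the authors intended, but the text does not say it. Footnote 12 states when a test is repeated. It does not state which value is the analysis baseline, and footnote 2 of the same table repeats the 96-hour limit for baseline information. SAP 10.2, where a laboratory exception would be expected, is silent. The SAP therefore carries both rules without ranking them.

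The second reply concerns consequence, and it stands. SAP 10.2 specifies descriptive statistics and shift tables, with no hypothesis test. Observed laboratory values at each time point and the adverse event tables need no laboratory baseline, so safety signals remain visible there.

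A reader might infer that many patients, or most, lose their laboratory baseline. The S = 7 row (43% at b = 0, and 71% at b = 2 or averaged over b from 0 to 4) could suggest this. Those figures describe the trial only if every patient is screened within 7 days of Baseline. Screening may be up to 28 days before Baseline, and anyone screened more than 7 days before has labs repeated. The documents do not show how large the within-7-days group is.

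**Conclusion.** The conflict is real on the wording of both documents, and it is also internal to the SAP. On a literal reading, some patients who followed the protocol exactly have no valid hematology or chemistry baseline.

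The number cannot be established. About 11% to 25% of patients rests on two assumptions: Screening uniform over the permitted 28 days, and a common Baseline-to-first-drug gap that runs from 0 to 4 days. Across other assumptions the range is 0% to 100%, so no claim that the number is large is supported.

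The effect is confined to the descriptive laboratory change-from-baseline and shift tables. The primary endpoint and the five hierarchical secondary endpoints do not depend on it. Whether a sample falls in the gap is decided by scheduling before the first dose of double-blind treatment, so no between-arm bias is expected. The cost is lost safety data and an avoidable ambiguity. The rule should be settled before the tables are produced.

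**What to change.** Add one sentence to SAP 3.4 or 10.2: for hematology and chemistry, baseline is the last value before the first of study drug, radiation or chemotherapy, including the Screening value where the 7-day rule did not require a repeat. Keep the 96-hour window for assessments always done at Baseline (WHO score, quality of life, pain and opioid history, vital signs).

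With this sentence the share of compliant patients caught between the two windows falls to zero. It needs no new data and no change to the visit schedule. The small downside is that some laboratory baselines will be up to 11 days old at first study drug, which the protocol's own windows already allow.

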## 4 SUBJECT DISPOSITION

The following subject data will be summarized:

- Number of subjects screened
- Number of subjects randomized but not treated
- Number and percentage of subjects in each analysis population
- Number and percentage of subjects who completed or prematurely discontinued. Subjects who prematurely discontinued the study will be summarized by primary reason for discontinuation.

#### 5 PROTOCOL DEVIATIONS

All instances of protocol non-compliance (protocol deviations [PDs]) will be tracked during study monitoring. Major PDs will be summarized by treatment group and category. Major PDs are those which may have an impact on the safety or protection of the subject, or impact the overall quality of the data. They may include, but are not limited to:

- Failure to obtain informed consent
- Failure to report an SAE
- Subject did not meet inclusion/exclusion criteria
- Drug dispensing/dosing errors

#### 6 DEMOGRAPHICS AND OTHER BASELINE CHARACTERISTICS

Demographic parameters and important baseline characteristics will be summarized by treatment group for the Safety, PP, ITT and mITT populations. Baseline characteristics include but may not be limited to age, age group, sex, country, ethnicity, race, weight, height, body mass index (BMI), HPV status, and presence of a gastrostomy tube at randomization.

Descriptive statistics of baseline values for other parameters such as vital signs, laboratory values, and efficacy parameters will be summarized with the post-baseline values in the corresponding safety and efficacy tables.

#### 7 MEDICAL HISTORY

Medical history will be coded using Medical Dictionary for Regulatory Affairs (MedDRA) version 20.0. Coded medical history terms will be summarized by system organ class (SOC) and preferred term (PT) for the Safety and mITT populations. At each level of summarization, subjects will only be counted once if multiple history items were recorded.

## 8 PRIOR AND CONCOMITANT MEDICATIONS

The World Health Organization Drug Dictionary (WHO Drug) version B3 2018 March 1st will be used to classify prior and concomitant medications by therapeutic class and generic name. Prior medication is defined as any medication taken prior to the first dose date of the study medication. Concomitant medication is defined as any medication taken between the day of first dose of the study medication or start of CRT (whichever is earliest) and 6 weeks after completion of RT. Medications taken before the first dose date and continued on or after the first dose date are categorized as both prior and concomitant medications.

Prior and concomitant medications will be summarized by the Anatomical Therapeutic Chemical (ATC) classification level 3 and generic name for the Safety and mITT populations. At each level of summarization, subjects will only be counted once if multiple drugs in that category are used.

Please see Appendix 1 for data handling conventions for any missing medication dates.

#### 9 EFFICACY ANALYSES

Efficacy will be conducted in the mITT population unless otherwise specified. Sensitivity analyses will include the same assessments in the ITT and PP populations.

#### 9.1 ANALYSIS OF PRIMARY ENDPOINT

As detailed in Table 2, the clinical evaluation of mucositis will be performed and graded by trained study evaluators in accordance with the WHO Oral Mucositis Grading system at each study drug administration visit and for Week 3 through Week 6 post-RT.

SOM is defined as OM with WHO Grade  $\geq 3$ . The duration of SOM is defined as the number of days from the first WHO score  $\geq 3$  to the first day with a WHO score  $\leq 3$  with no further occurrence of a WHO score  $\geq 3$ . A log-rank test will be used to compare the duration of SOM of the two treatment groups.

Resolution of SOM is defined as the first assessment with a WHO score <3 with no further reports of a WHO grade of  $\ge 3$ . If the patient has not met the requirements for resolution of SOM by the 6-week post-RT visit, he/she will be considered censored at that visit (or the point of discontinuation from the study, if the patient discontinues prior to that time point). For statistical reasons, patients who do not experience SOM will be treated as having a duration of 0.01 days.

Possible scenarios for onset of SOM are displayed below in Figure 2, along with the derivation of duration of SOM.

[figure not shown]

Figure 2: Duration of SOM (Primary Analysis)

